### 6.5.2 Clinical Laboratory Evaluation

The baseline value will be the last non-missing value taken on or prior to first dose of study drug. In the "Schedule of Assessment" table in the protocol (Table 1) this "baseline" assessment will be done at screening (Visit 1).

In the eCRF both Blood Urea and Blood Urea Nitrogen (BUN) are presented. In the event that Blood Urea is measured and not BUN, then for summary statistics the BUN value will be obtained using the following formulae:  $BUN(mmol/L) = 2.1428 \times Urea(mmol/L)$  Note: BUN values will be summarized and in the listing both Blood Urea and BUN values will be presented.

When corrected serum calcium is not measured, the corrected serum calcium will be calculated as (depending on the units used for calcium and albumin): Corrected calcium (mmol/L) = measured total Ca (mmol/L) + 0.02 [40 (g/L) - albumin (g/L)])

For each local laboratory, separately, the quantitative clinical laboratory variables, i.e., hematology, biochemistry, and urinalysis, will be summarized using mean, standard deviation, median, minimum and maximum by treatment group and visit [visits 1 and 5] and for EoT values.

In addition, data from the local laboratories will be normalized to a single laboratory for the purpose of combining all laboratories and providing an overall summary. For normalizing the data of a laboratory parameter a common reference range for this parameter has to be determined. In this study the common reference range is the normal range coming from the site with the highest number of treated subjects.

Calculating the normalized value of a laboratory parameter: first all data from the parameter assessed in the local laboratories will be transformed into SI units. Next the data will be transformed according to the transformation formula below. Let x be the value of the laboratory parameter from the local laboratory, ULNL the upper limit of the normal range of the local laboratory, and ULNC the upper limit of the common reference range, then the transformed value (t) from the local laboratory is:

 $t = x. \frac{ULNC}{ULNL}$  (Scale normalization, Karvanen et al.)

This value t will be used for reporting normalized laboratory values. Both the observed and normalized values (where applicable) will be reported in listings.

Additionally, for groups with both a baseline and week 12 measurement (i.e., Mirabegron 25 mg [Never Up-Titrated], Mirabegron 50 mg [As-Randomized] and Total Mirabegron) a within-subject change will be calculated as the post-baseline measurement minus the baseline measurement and summarized in the same way. Each laboratory result will be classified as low (L), normal (N), or high (H) at each visit according to the laboratory supplied reference ranges.

The number and percentage of subjects below and above reference range will be summarized by treatment group and visit.

Frequency tabulations of qualitative clinical laboratory variables (urinalysis) will be presented by treatment group and visit.

Summary shifts of reference range (low, normal, high) changes from baseline to week 12 will be presented by the following treatment groups:

- Mirabegron 25 mg (Total)
- Mirabegron 50 mg (As-Randomized)
- Total Mirabegron, i.e., the sum of the Mirabegron 25 mg (Total) and of Mirabegron 50 mg (As-Randomized).

These shifts are categorized as:

- "Shift to Low": shift from normal or high to low
- "Shift to High": shift from normal or low to high
- "Categorized Increase": shift from low to normal or from normal to high
- "Categorized No Change": value stays in the same reference range
- "Categorized Decrease": shift from high to normal or from normal to low.

All clinical laboratory data collected during the study and variables derived from it will be listed using SAF.

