10.6 Appendix 6: Clinical Laboratory Assessments

Laboratory tests will be performed according to the Schedule of Assessments [Table 1] and sent to a local laboratory for analysis.

Panel/Assessments	Parameters to be Analyzed
Hematology	Hematocrit
	Hemoglobin
	Mean corpuscular volume
	Mean corpuscular hemoglobin
	Mean corpuscular hemoglobin concentration
	Platelets
	Red blood cell count
	White blood cell count
	White blood cell count differential
Biochemistry	Albumin
	Alanine aminotransferase
	Alkaline phosphatase
	Aspartate aminotransferase
	Bicarbonate
	Blood urea nitrogen
	Calcium
	Chloride
	Corrected serum calcium
	Creatinine
	Creatinine kinase
	Glucose
	Lactate dehydrogenase
	Magnesium
	Phosphate
	Potassium
	Sodium
	Total bilirubin (total and direct)
	Total protein
Uninclusia	
Urinalysis	Leukocyte esterase Nitrites
	pH
	Protein
	Red blood cells
	Human chorionic gonadotropin (female subjects only)
Serology (Plasma/serum)	HAV antibodies (IgM)
	HBsAg
	HBc antibodies
	HCV antibodies
	HIV antibodies
	Syphilis

Table 7Clinical Laboratory Tests

HAV: hepatitis A virus; HBc: hepatitis B core; HBsAg: hepatitis B surface antigen; HCV: hepatitis C virus; HIV: human immunodeficiency virus; IgM: immunoglobulin M

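### The SAP derives BUN by multiplying urea in mmol/L by 2.1428, a mass ratio that does not apply between molar units and runs the wrong way, so derived BUN is too high (2.14-fold under the usual convention)

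*SAP*

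**What the plan says.** BUN belongs to the biochemistry panel: "Blood urea nitrogen" is listed in protocol section 10.6 (Appendix 6), and SAP Table 4 repeats it. Testing is done at local laboratories (protocol 7.2.1, SAP 5.4.3), and SAP Appendix 9.1 gives 15 randomizing sites.

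SAP section 6.5.2 notes that the eCRF has fields for both blood urea and BUN. It then gives a rule for records with urea only: "In the event that Blood Urea is measured and not BUN, then for summary statistics the BUN value will be obtained" from "BUN(mmol/L) = 2.1428" multiplied by urea, with urea also stated in mmol/L. On output, "BUN values will be summarized and in the listing both Blood Urea and BUN values will be presented".

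Two later steps in the same section use laboratory limits:

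- **Normalization.** For pooling, "first all data from the parameter assessed in the local laboratories will be transformed into SI units". Each value is then multiplied by ULNC/ULNL, the common upper limit over the local upper limit.
- **Classification.** "Each laboratory result will be classified as low (L), normal (N), or high (H) at each visit according to the laboratory supplied reference ranges".

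The SAP gives no source for the factor and does not define BUN in mmol/L. It does not say whether a urea reference limit is converted along with the value. No other section corrects the formula.

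**The concern.** The formula carries mmol/L on both sides, yet the factor is recognizable as a ratio of masses. A mass ratio cannot link two molar concentrations of the same substance. Even as a mass conversion it points from BUN to urea, the reverse of what is needed here.

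Section 6.5.2 makes BUN, not urea, the summarized parameter, so the derived value is the one that reaches the safety tables. Laboratory tests are a secondary safety endpoint in a study meant to support licence renewal and safety surveillance. Programmed as written, the rule could show implausibly high BUN at laboratories that report urea only. It would also put values on two different scales under one parameter name.

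**Working it through.** **Inputs.** The factor 2.1428 and both units come from SAP 6.5.2. Molecular masses are basic chemistry, not taken from the documents: urea 60.056 g/mol (about 60), two nitrogen atoms 28.014 g/mol (about 28).

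**Step 1: where 2.1428 comes from.** 60/28 = 2.142857, which truncates to 2.1428. With the fuller masses, 60.056/28.014 = 2.1438. The factor is the mass of urea per mass of urea nitrogen.

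**Step 2: what the factor should be.**

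| Conversion | Correct factor | SAP factor / correct factor |
|---|---|---|
| Urea mmol/L to BUN mmol/L, usual convention (one per urea molecule) | 1 | 2.14 |
| Urea mmol/L to BUN mmol/L, counting nitrogen atoms | 2 | 2.1428/2 = 1.071 |
| Urea to BUN, both in mass units | 28/60 = 0.467 | 4.59 |
| BUN to urea, both in mass units | 60/28 = 2.143 | 1.00 |

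Only the last row reproduces the SAP's number. It has the wrong units and the wrong direction for this use.

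**Step 3: cross-check on one sample.** Urea of 60 mg/dL is 600 mg/L, and 600/60 = 10 mmol/L. The same sample has BUN of 28 mg/dL, or 280 mg/L, and 280/28 = 10 mmol/L under the usual convention. The SAP formula gives 10 × 2.1428 = 21.4.

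**Step 4: effect on values and changes (usual convention).** Urea of 3, 5 and 7 mmol/L becomes 6.4, 10.7 and 15.0. A true change of 0.5 becomes 0.5 × 2.1428 = 1.07.

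**Step 5: normalization.** Take urea 5 with ULNL = ULNC = 8 (assumed limits).

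- Local limit left as the urea limit: 10.71 × 8/8 = 10.7.
- Local limit multiplied by the same factor: 10.71 × 8/(8 × 2.1428) = 5.0, so the error cancels.

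**Step 6: pooled mean.** Let f be the share of subjects with urea only, with limits not converted and with equal true means and equal upper limits. The pooled mean is then multiplied by 1 + f × 1.1428. The documents do not give f; for assumed shares of 5%, 10%, 25% and 50% the mean is 6%, 11%, 29% and 57% too high.

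**Step 7: classification.** If derived BUN were compared with an unconverted urea limit, a result would be High once urea exceeds 1/2.1428 = 47% of that limit. For assumed limits of 7, 8 and 9 mmol/L, the thresholds are 3.3, 3.7 and 4.2 mmol/L. If the reported urea is classified against its own range, nothing changes.

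**The case against.** The formula itself cannot be defended, but its size and reach can be argued down.

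- **Size.** The SAP does not define BUN in mmol/L, so the 2.14-fold figure rests on an outside convention. If nitrogen atoms are counted, the error is 7%. This stands: the supportable range is 7% to 114% too high, and the formula is wrong at both ends.
- **Classification.** The derived value is introduced for summary statistics, while the classification rule refers to each laboratory result and the range that laboratory supplies. A urea-only laboratory supplies urea and a urea range, so the low/normal/high counts and shifts may well be unaffected. This also stands, and is why that effect is only conditional. The SAP should still say which value is classified.
- **Pooled figures.** Step 6 stacks several assumptions. It shows scale and is not an estimate.
- **Within one laboratory.** Where a laboratory reports only urea, all its BUN values are multiplied by one constant. Signs, relative changes and ratios between dose groups are preserved. That is true, but absolute levels and changes are what the tables display.
- **Consequences.** Laboratory data are summarized descriptively. BUN is not an eligibility threshold, a specified discontinuation criterion, an adverse event of special interest or a liver criterion. Recorded urea is listed, so the error can be traced and reversed. All of this limits the severity, but none of it makes the derivation correct.

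**Conclusion.** The concern holds. The conversion in SAP 6.5.2 is wrong under either meaning of BUN in mmol/L: 2.14 times too high under the usual convention, 7% too high if nitrogen atoms are counted.

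The firm consequence is that, for any subject with urea but no BUN, the derived observed BUN values, the by-laboratory summaries and the changes from baseline are wrong. Distortion of the normalized overall summary and of the low/normal/high results is conditional: it needs derived BUN to be used with an unconverted urea limit, a point the SAP leaves open.

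The documents do not give the number of affected subjects. It could be zero, since the panel names BUN, although the SAP provides for urea-only records. The primary efficacy analysis and the sample size are not affected. This should be fixed, but it does not threaten the study's main conclusion.

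**What to change.** In SAP 6.5.2:

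1. Replace the formula with BUN (mmol/L) = Urea (mmol/L), and state that BUN in mmol/L is expressed per mole of urea.
2. For a laboratory reporting mass units, use BUN (mg/dL) = Urea (mg/dL) / 2.14 before conversion to SI units.
3. State that the same conversion is applied to that laboratory's reference limits before low/normal/high classification and before ULN normalization.
4. Report the number of subjects with derived BUN.

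The cost is one formula and one sentence in the SAP, plus the matching lines of the derivation program. No new data are needed, because the recorded urea values are kept.

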## 5.4.3 Clinical Laboratory Variables

Hematology, biochemistry and urinalysis assessments will be taken at visit 1/week -2 (screening), and visit 5/week 12 (EoT).

All clinical laboratory assessments will be performed at a local laboratory. Urine pregnancy tests (female subjects of childbearing potential only) will be performed according to the clinical site's preferred method at visit 1/week -2 (screening) and visit 5/week 12 (EoT) except for cases in which the possibility of pregnancy was clearly ruled out by hysterectomy, bilateral oophorectomy or the passage of 2 or more years after last menstruation.

A blood sample will be collected for serology tests (HAV antibodies [IgM], HBc antibodies, HBsAg, HCV antibodies, syphilis and antibodies to HIV types 1 and 2) at screening only.

Additional hematology, biochemistry and urinalysis (UA dipstick) tests may be performed at visit 1/week -2 (screening) and visit 5/week 12 (EoT). If any of the clinical laboratory tests results are outside the normal range at any scheduled time point during the study, the investigator may decide to repeat the test(s) on new samples. The clinical relevance of the abnormal results will be documented. Clinically relevant changes will be recorded as AEs (see Section 7.3 of protocol).

The laboratory parameters that will be assessed during the conduct of the study are listed in Table 4.

Hematology	Biochemistry	Urinalysis	Serology*
Hematocrit	Albumin	Leukocyte esterase	HAV antibodies
Hemoglobin	Alanine aminotransferase	Nitrites	(IgM)
Mean corpuscular volume	Alkaline phosphatase	pH	HBsAg
Mean corpuscular	Aspartate aminotransferase	Protein	HBc antibodies
hemoglobin	Bicarbonate	Red blood cells	HCV antibodies
Mean corpuscular	Blood urea nitrogen	Human chorionic	HIV antibodies
hemoglobin concentration	Calcium	gonadotropin (female	types 1 and 2
Platelets	Chloride	subjects only)	Syphilis
Red blood cell count	Corrected serum calcium		
White blood cell count	Creatinine		
White blood cell count	Creatinine kinase		
differential	Glucose		
	Lactate dehydrogenase		
	Magnesium		
	Phosphate		
	Potassium		
	Sodium		
	Total bilirubin (total and		
	direct)		
	Total protein		

Table 4Laboratory Assessments

\* Serology parameters will be only collected at screening.

The value of each hematology and biochemistry parameter will be compared to its normal range and classified as High, Low or Normal. Urinalysis parameters will be similarly classified as either Normal or Abnormal.

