### 5.4.5 12 Lead ECGs

A 12-lead ECG will be performed as single measurement at visit 1/screening and visit 5/week 12 (EoT). ECG traces will be evaluated by the investigator who will give an overall interpretation and may leave a qualifying comment in the eCRF. The overall interpretation will be recorded as:

- Normal, or
- Abnormal not clinically significant, or
- Abnormal clinically significant

As well as the overall interpretation, the following ECG variables will be supplied by the local laboratory: PR Interval (msec), RR Interval (msec), QRS Duration (msec), QT interval (msec) and Heart Rate (HR) (beats/min).

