### 6.5 Analysis of Safety

Safety analysis will be conducted on the SAF. Safety endpoints will be summarized by treatment group and visit, if applicable. Descriptive statistics will be presented.

All safety summaries (except for shift tables in Sections 6.5.2 and 6.5.4) will be presented by the following:

- Mirabegron 25 mg
  - Never Up-Titrated
  - Later Up-Titrated to 50 mg (at visit 3 or 4)
  - Total
- Mirabegron 50 mg
  - $\circ$  as Randomized
  - Up-Titrated from 25 mg (at visit 3 or 4)
  - Total
- Total Mirabegron, i.e., the sum of the Mirabegron 25 mg (Total) and of Mirabegron 50 mg (As-Randomized)

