#### 6.5.4 Electrocardiograms

The baseline value will be the last non-missing value taken on or prior to first dose of study drug. In the "Schedule of Assessment" table in the protocol (Table 1) this "baseline" assessment will be done at screening (Visit 1).

ECG variables will be summarized using mean, standard deviation, median, minimum, and maximum by treatment group total and visit, including changes from baseline for groups with both a baseline and week 12 measurement. Summary of ECG variables will be presented for each visit [visits 1 and 5], and for EoT values. In addition to the ECG variables mentioned in Section 5.4.5, QTcF (msec) (=QT (msec)/([RR (msec)/1000]1/3) will be summarized. Note: unit for QT and RR reported in CRF is msec.

Normal, not clinically significant abnormal, and clinically significant abnormal results as assessed by investigator for the 12 lead ECG along with shift tables will be presented for changes from baseline to Week 12 including local interpretation categories by the following treatment groups:

- Mirabegron 25 mg (Never Up-Titrated)
- Mirabegron 50 mg (As-Randomized)
- Total Mirabegron.

The QTc interval will be summarized using frequency tables for each treatment visit and time point for values of clinical importance using the range criteria below.

Category	QTc Interval Criteria Value (msec)	
Normal	$\leq$ 450	
Borderline	> 450	
Prolonged	> 480	
Clinically significant	> 500	

Note that these categories are cumulative in that subjects satisfying criterion for more extreme category will also be counted in each applicable less extreme category.

The corrected QT interval (i.e., QTcF) will also be summarized by treatment group and visit showing the frequencies of subjects with the following changes from baseline:

Variable	Change from Baseline
QTc Interval (msec)	< 0
	$\geq 0$ and $< 30$
	$\geq$ 30 and < 60
	$\geq$ 60

ECG data will be provided in listing format by site and subject for the SAF.

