For non-diary data, if a subject has more than one non-missing value within a visit window, the non-missing assessment which is closest to the target day within a window will be used. If two or more values are equally close and on different days, the latest non-missing value will be used. If two or more values are equally close and on the same day, the mean will be used for continuous variables or the worst observed case for categorical variables.

For diary data, the assessment date for the whole diary will be considered to be the date of the last valid day of the diary. If more than one diary has an assessment date within the same window, and if this results in more than one non-missing value of a diary variable, the non-missing value with the diary assessment day that is closest to the target day will be used. In case of ties on different days, the later non-missing value will be used. In case of ties located on the same side of the target day (i.e., more than one value for the same day), the mean of the values will be used for continuous variables and the worst value for categorical variables.

For analyzing diary data the labels of the study visits will not be used, they will be assigned based on the dates of assessment.

A two-day window around the visit date will be applied for the assignment of study period for exposure data.

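### The lab shift, lab change and ECG shift tables place dose-escalated subjects inconsistently, and none of their group lists gives those subjects a row

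*SAP*

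**What the plan says.** SAP 6.5 sets a general layout for safety output: 25 mg (Never Up-Titrated, Later Up-Titrated, Total), 50 mg (As-Randomized, Up-Titrated from 25 mg, Total), and a pooled column. It makes one exception: "All safety summaries (except for shift tables in Sections 6.5.2 and 6.5.4) will be presented by the following". The pooled column is defined as "Total Mirabegron, i.e., the sum of the Mirabegron 25 mg (Total) and of Mirabegron 50 mg (As-Randomized"), and the lab shift list in 6.5.2 repeats that definition.

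Three tables then carry their own group lists:

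- **Lab shifts, baseline to Week 12 (6.5.2):** "Summary shifts of reference range (low, normal, high) changes from baseline to week 12 will be presented by the following treatment groups". The groups are 25 mg (Total), 50 mg (As-Randomized) and Total Mirabegron.
- **Lab change from baseline (6.5.2):** restricted to groups that have both a baseline and a Week 12 value, "i.e., Mirabegron 25 mg [Never Up-Titrated], Mirabegron 50 mg [As-Randomized] and Total Mirabegron) a within-subject change will be calculated".
- **ECG shifts, baseline to Week 12 (6.5.4):** "Mirabegron 25 mg (Never Up-Titrated"), 50 mg (As-Randomized) and Total Mirabegron.

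On timing, SAP 5.4.3 says: "Hematology, biochemistry and urinalysis assessments will be taken at visit 1/week -2 (screening), and visit 5/week 12 (EoT"). SAP 5.4.5 says: "A 12-lead ECG will be performed as single measurement at visit 1/screening and visit 5/week 12 (EoT"). Escalation from 25 mg to 50 mg is allowed at Week 4 or Week 8 (SAP 2.2). In SAP Table 5 the Week 12 window for labs and ECG runs from Day 2 to Day 97 with target Day 84. When several values fall in the window, "the non-missing assessment which is closest to the target day within a window will be used".

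**The concern.** An escalated subject has no scheduled on-treatment lab or ECG value while on 25 mg. The only scheduled post-baseline value comes at Week 12, after the switch. The SAP appears to recognise this for lab change and ECG shifts, where the 25 mg row is limited to subjects who never escalated. The lab shift table does not follow that logic, and no reason is given.

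Two things are at stake. A reader of the lab shift table cannot tell whether a shift in the 25 mg row arose on 25 mg or on 50 mg. Nor can a reader assume that the 25 mg rows of the lab and ECG shift tables describe the same subjects. Safety is a secondary objective, the study supports the licence renewal, and the regulator asked about dosage including the initiation dose (Protocol 2). The dose on which a shift arose therefore bears on the study's purpose.

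**Working it through.** **Step 1. The lists side by side.**

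| Table | 25 mg row | 50 mg row | Row for escalated subjects | Covered by the 6.5 exemption? |
|---|---|---|---|---|
| Lab shifts (6.5.2) | Total | As-Randomized | none | yes |
| Lab change (6.5.2) | Never Up-Titrated | As-Randomized | none in its list | no |
| ECG shifts (6.5.4) | Never Up-Titrated | As-Randomized | none | yes |

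The exemption covers both shift tables alike, so it cannot explain why their 25 mg rows differ. Lab change is not a shift table. The general layout, with its up-titrated columns, therefore nominally governs it, and the shorter list in 6.5.2 conflicts with 6.5.

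**Step 2. The dose at the Week 12 value.** Escalation is at Week 4 or 8. The lab window is wide, but the value nearest Day 84 is chosen, which is normally the Visit 5 value. For an escalated subject that value is on 50 mg. An unscheduled test before the switch would be used only if nothing nearer to Day 84 existed.

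**Step 3. Two readings of 25 mg (Total) in the lab shift table.**

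- *Reading A: everyone randomized to 25 mg.* The row contains Week 12 values taken on 50 mg, and it is not the same group as the ECG 25 mg row.
- *Reading B: data while on 25 mg only.* Escalated subjects have no scheduled Week 12 value to contribute. They fall out of the 25 mg row and, because the Total in this table is defined as 25 mg (Total) plus 50 mg (As-Randomized), out of the Total as well.

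**Step 4. Size.** Inputs are 249 subjects randomized 2:1 (Protocol 1.1), so 249/3 = 83 on 25 mg and 166 on 50 mg. The documents give no escalation rate; q = 10%, 25% and 50% are assumptions. Dropout is ignored.

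| | q = 10% | q = 25% | q = 50% |
|---|---|---|---|
| Escalated, 83 × q | 8.3, about 8 | 20.75, about 21 | 41.5, about 42 |
| Share of all subjects, 83q/249 | 3.3% | 8.3% | 16.7% |
| Never up-titrated, 83 − escalated | 75 | 62 | 41 |
| ECG shift dose rows, never up-titrated + 166 | 241 | 228 | 207 |
| Reading A: lab shift 25 mg row | 83 | 83 | 83 |
| Reading A: of these, Week 12 value on 50 mg | 8 | 21 | 42 |
| Reading B: lab shift Total | 241 | 228 | 207 |

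Under A the lab and ECG 25 mg rows differ by 8, 21 or 42 subjects. Under B the lab shift Total falls short of 249 by the same numbers. SAP 6.5.4 does not define its own Total, so I draw no count for it.

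**The case against.** The best reply is that 25 mg (Total) may simply mean data while on 25 mg. SAP 6.4.1.1 uses the label that way for efficacy, where post-switch data are left out of the model. The lab and ECG 25 mg rows would then hold nearly the same subjects, and no 50 mg value would sit in a 25 mg row. That is correct, and it means the comparability problem belongs to Reading A only. It does not remove the defect, because under Reading B the escalated subjects leave the lab shift table altogether. Under Reading A, the row sits badly with the rule in SAP 4.4 that the safety set is analysed by treatment received.

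A second reply is that escalated subjects are visible elsewhere. This stands. The counts of values outside the reference range, the QTc categories and the other by-visit summaries are not shift tables, so the 6.5 layout gives them up-titrated columns, and all data are listed. A reader might infer that escalated subjects vanish from safety reporting; the documents do not support that. A reader might also infer that the lab change table certainly has no column for them. That is not established either, since 6.5 and 6.5.2 conflict on this table.

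A third reply is that column layouts may be settled in the TLF specifications, which SAP 6.1 mentions and which are not among the documents. They may be, but the SAP's own lists would still disagree.

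**Conclusion.** The plan is wrong as written, and the point is minor. The label conflict and the missing row are plain in the text and need no assumption. The number of subjects affected does: about 8, 21 or 42 of 83 at assumed escalation rates of 10%, 25% or 50%, before dropout.

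Three stronger inferences are not supported:

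- **A biased 25 mg versus 50 mg safety comparison.** The SAP plans none for labs or ECG; safety is descriptive.
- **Post-escalation data missing from Total Mirabegron throughout the safety output.** SAP 6.2 uses the same sum as a head count of the whole population (83 + 166 = 249), so all data may be intended. The omission follows only for the lab shift table, and only under Reading B.
- **Counts reduced by the planned 25% dropout.** Protocol Table 1 asks early withdrawals who received study drug to attend the EoT visit, and the lab window opens on Day 2, so dropouts may still supply a value. The 25% was also planned for the 50 mg group.

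The primary 50 mg analysis is not affected.

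**What to change.** Use one row set in the lab shift, ECG shift and lab change tables:

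1. 25 mg Never Up-Titrated.
2. 50 mg As-Randomized.
3. Up-Titrated from 25 mg to 50 mg, with a footnote that the change from Visit 1 spans both doses.
4. Total Mirabegron, with each subject counted once.

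Reconcile the lab change list in SAP 6.5.2 with the general layout in 6.5, so that one of them clearly governs.

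The cost is SAP wording and table-shell edits. No new data or visits are needed.
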